### 5.3.1 Patient selection period

The study period will be from the earliest data availability to the latest data availability based on the eligible patients identified. The PEDSnet CDM includes any person with at least one encounter with the member health system after December 31, 2008 which included a visit with a clinician; and one or more coded diagnoses were recorded in the person's record after December 31, 2008. For persons meeting these criteria, any available data is included in the PEDSnet CDM, including data earlier than 2009.

The study period will not be restricted by the FDA approval date for LCM, as it occurred in 2008 before the earliest date of data availability in the PEDSnet database.

The exposure to IV LCM will be defined by the presence of RxNorm codes for generic or brand name of IV formulations of LCM as indicated below in Section 5.5.4.

The index date for the higher IV LCM cohort will be the earliest of either of the following identified during the study period and with the required 3-month baseline period:

- a new treatment episode for an IV LCM dose (as described in Section 5.2 ); or
- receipt of a first higher IV LCM dose than known maintenance dose (as described in Section 5.2 .

The index date for the recommended initial dosage/maintenance IV LCM cohort will be the earliest of the following identified during the study period and with the required 3-month baseline period:

- a new treatment episode corresponding to an recommended initial dosage or a slow up-titration (as described in Section 5.2 )

IV LCM is usually administered in an inpatient setting for treatment of severe seizure conditions. We therefore anticipate the level of detail recorded for clinical information for the patients treated with IV LCM will be comprehensive as most of the patients will be treated in an inpatient setting.

### 5.3.2 Baseline (pre-index) period

The baseline period for this study will be the 3 months prior to either the first newly initiated qualifying treatment episode of a higher IV LCM dose or a recommended initial IV LCM dose; for patients less than 3 months of age at index event, the baseline period will be birth through index event.

Data from the baseline period will be used to determine the indications for LCM and to define a new treatment episode. All available data prior to the index date will be used to evaluate the patient characteristics, diagnosis, procedures, and medications administered, dispensed or prescribed (AEDs, benzodiazepines and non-AEDs) medications, and identify preexisting

conditions of interest, if any. Preexisting medical events of interest are not exclusion criteria in this study; instead, they will be used to characterize the patient population. Section 5.5.6 details pre-existing medical events of interest that will be evaluated during the baseline period.

Potential indications for IV LCM include but are not limited to epilepsy, febrile seizures, and status epilepticus. The indications in both the higher and recommended IV LCM cohorts will be classified as follows:

- Patients with only one of the listed potential indications in the baseline period will be assigned the identified indication
- Patients with none of the listed potential indications in the baseline period will be classified as having other indications
- Patients with more than 1 of the listed potential indications in the baseline period will be classified as having multiple indications.

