### 5.5.3 Other variables - baseline characteristics

During the baseline period, patient characteristics (e.g. age at index date, gender, ethnicity, PEDSnet health system site, weight), clinical characteristics (i.e. number of previous AEDs and concomitant medications prescribed prior to the index date [AEDs, benzodiazepines and non-AEDs], prevalence of comorbidities, medical procedures such as EEG) will be evaluated. Baseline data will be assessed for IV LCM exposure indications, dosage of IV LCM and preexisting medical events of interest (i.e. cardiac conditions, dermatologic conditions, vascular conditions, injury, poisoning and procedural complications, general disorders and administration site conditions, investigations, drug reaction with eosinophilia and systemic symptoms syndrome, severe cutaneous adverse reactions, hypersensitivity events).

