**Table 4 Measures available in the PEDSnet database**

Domain	Type of Data
Demographics	Age, date of birth, gestational age, sex, ethnicity, race, zip code, PEDSnet health system site, primary care provider, death and cause of death (if available)
Outpatient encounters (~75 visit specialty types available)	Primary care visits, specialty care clinics (e.g., cardiology, endocrinology, nephrology, oncology, etc.), physical therapy, occupational therapy, speech language pathology, medical genetics/genomics, etc.
Inpatient admissions	Length of stay, discharge status; diagnoses, procedures, medications, and lab results associated with inpatient stay
Emergency department encounters	Diagnoses, procedures, medications, and lab results associated with emergency department visit; emergency department visits resulting in inpatient admission
Anthropometrics	Height (cm) and weight (kg), body mass index, head circumference
Vital signs	Temperature, blood pressure
Providers	Specialty, health care facility
Diagnoses	Final diagnoses are recorded at each encounter and are mapped to a standardized codes (typically SNOMED-CT)

Domain	Type of Data
Procedures	Procedures are recorded at each encounter and are mapped to standardized SNOMED-CT, ICD-9 Procedure, ICD-10 Procedure, CPT-4, and HCPCS codes
Prescribed medications	Medications ordered are recorded at each encounter and mapped to a standardized RxNorm code
Dispensed medications	Medications dispensed, when available, are recorded and mapped to a standardized RxNorm code
Laboratory test results	Contains the orders and results for more than 400 laboratory tests. Examples include key components of lipid panel, complete metabolic panel, complete blood counts, microbiologic cultures, liver function tests, urinalysis, viral panels, etc.
Visit payer	Plan class (private/commercial, medicaid/sCHIP, Medicare, other public, self-pay, other/unknown), plan type (HMO, PPO, POS, fee for service, other/unknown) for every unique visit. Enrollment information unavailable.

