#### 5.9.1.1 Adjustment for baseline characteristics using propensity scores

We will use propensity score and inverse probability of treatment weights (IPTW) to control confounding (Brookhart 2013). The propensity score will be estimated using a logistic regression model, in which higher IV LCM dose (vs. recommended initial/maintenance IV LCM dose) will be regressed on the baseline characteristics. Covariates for inclusion in the propensity score model were selected based on their potential association with the outcomes, including patient characteristics, patient disease history, and treatment history, as indicated on page 35 of the study protocol under section 5.6.6, and on page 21 section 5.6.3 of the protocol, and as listed below:

- Weight
- Sex
- Age at time of seizure treated with loading dose
- Ethnicity (if available)
- PEDSNet site
- Diagnosed medical conditions
- Prior AED/benzodiazepine prescribing (home use) or administration in hospital
- Prior seizure number if available
- Treatment for said seizures (AED and/or benzodiazepine)
- Concomitant prescribing
- Pre-existing medical conditions of interest for the safety evaluation: cardiac conditions, dermatologic conditions, vascular conditions, injury, poisoning and procedural complications, general disorders and administration site conditions, investigations, drug reaction with eosinophilia and systemic symptoms syndrome, severe cutaneous adverse reactions, hypersensitivity events
- Prior EEG data at last seizure

After the propensity scores have been generated, we will assess for violations of underlying assumptions. Positivity violations will be assessed by plotting the propensity score distributions in an overlay plot for the comparator groups. To evaluate adequate overlap of the propensity scores, we will visually inspect the density distribution of the propensity scores (Rosenbaum and Rubin, 1984). The performance of the model will be evaluated by assessing the covariate balance across the treatment groups. Standardized differences will be used to compare the mean or prevalence of baseline covariates between the comparator treatment groups in the samples

weighted by the inverse probability of treatment. Additionally, continuous variables will be compared using graphical methods including boxplots and nonparametric density plots.

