### **5.9.2 Handling of Missing Data**

Data is dependent on information that was recorded by physicians and nurses into the EHR. It is therefore assumed that the patient did not have the diagnosis of interest if it is not reported in the EHR. No missing data will be imputed. For demographic characteristics, the type of missingness will be evaluated.

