### 5.9.4 Strength and Limitations

**Unmeasured confounding:** As the study is comparing the incidence rates of select medical events in patients who are treated with a high dose of IV lacosamide to patients who are treated with recommended dose of IV lacosamide, the major confounders are factors that impact the incidence rate of these medical events of interest. These factors include age, gender, comorbidities, and exposure to other medications which are measured. Unmeasured confounding would only occur if there was a major confounder which is not measured and thus missed from the adjusted model. However, the electronic medical records include demographic information, the medical history of the patients and any medications prescribed by the physicians. Therefore we anticipate that information on most of the confounders will be available. It is possible that there will be missing information on some comorbidities, if they are not recorded by the physicians and on medications that are either bought over counter or prescribed outside the PEDSnet healthcare network. Nevertheless, most hospitals in the PEDSNet healthcare network are large with epilepsy comprehensive care centers within the neurology departments, so we anticipate reliable background medical. We do not anticipate that there will be a disproportionate difference in the recording of the medical history data and prescription of medications in patients who are treated with high dose lacosamide and recommended lacosamide prior to the index date. Therefore, we anticipate that there will be minimal unmeasured confounding. Additionally, the analysis will be using new user design to minimize confounding by indication.

**Reduced generalizability:** The PEDSnet database is restricted to subjects seeking and receiving medical care within a facility affiliated with PEDSnet. Data is obtained from multiple care sites and type (e.g. in-patient, out-patient, emergency department). However, if a report of an event was made or a subject was treated for an event at a facility that is not affiliated PEDSnet, this information will not be captured in the PEDSnet data. However, as most events are anticipated to occur within 24 hours of receiving IV LCM, the impact of this is likely to be low.

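### The propensity score has no term for prior network contact, so history not recorded before the first IV dose counts as absent; if first-contact shares differ by dose group, the weighted IRR is biased in an unknown direction.

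*Protocol*

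**What the plan says.** Five parts of the protocol combine here.

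- **Look-back.** Section 5.3.2: "All available data prior to the index date will be used to evaluate the patient characteristics, diagnosis, procedures, and medications administered". Section 5.5.3 points instead to the 3-month baseline: "During the baseline period, patient characteristics (e.g. age at index date, gender, ethnicity, PEDSnet health system site, weight". Neither sets a minimum amount of recorded history.
- **Absent records.** Section 5.9.2: "It is therefore assumed that the patient did not have the diagnosis of interest if it is not reported in the EHR", and "No missing data will be imputed". No other rule is given for covariate diagnoses.
- **Eligibility.** Sections 5.2.1 and 5.2.2 ask for one IV lacosamide administration in the age range and no lacosamide in the preceding 3 months. An empty record meets both. Section 5.3.1 calls the 3-month baseline required but does not define it by any observed encounter. Table 4 adds, on visit payer data, "Enrollment information unavailable", so a child treated elsewhere and a child with no illness look the same.
- **Propensity score.** Section 5.9.1.1: "Covariates for inclusion in the propensity score model were selected based on their potential association with the outcomes". Its list includes diagnosed conditions, prior AED or benzodiazepine use, prior seizure number if available, prior EEG and "Pre-existing medical conditions of interest for the safety evaluation". It has no term for earlier encounters or length of record.
- **Defence.** Section 5.9.4 concedes that some comorbidities and outside prescriptions may be missing, then states: "We do not anticipate that there will be a disproportionate difference in the recording of the medical history data" between dose groups. No check of that statement is planned.

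**The concern.** A child with years of network records and no recorded comorbidity is known to be fairly healthy. A child first seen at the index admission, with the same blank entries, is of unknown health. The score gives both the same covariate values and treats them as exchangeable.

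If first-contact children are more frequent in one dose group, that group carries more hidden illness among those coded healthy, and part of the illness effect is credited to dose. The IRR is a primary measure in section 5.5.1, so this bears on the main comparison. The standardised differences in 5.9.1.1 compare the same incompletely recorded covariates, so they can look good while true illness differs.

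The sensitivity analyses in 5.9.1.4 do not reach the problem. A 6-week baseline still requires no earlier encounter. Excluding children with pre-existing events keeps first-contact children unless something was recorded earlier in the index stay.

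**Working it through.** The protocol gives no figure on this point to reproduce; the 875 in section 5.9.3 is a feasibility count. What follows is an illustration with **every input assumed**.

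**Set-up.** True dose IRR 1; equal group sizes and follow-up; one comorbidity.
- p = comorbidity prevalence in a dose group: 40% or 50% in both, or 50% (high dose) v 30% (recommended).
- u = first-contact share: 25% v 10%, or 40% v 15% (high v recommended).
- RR = event rate ratio for the comorbidity: 2 or 3.
- c = share of first-contact children's illness recorded before the index dose: 0, 0.5 or 0.8. Illness is fully recorded in the other children.

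**Formulas, per dose group.**
- Recorded as ill: r = p × [1 − u(1 − c)].
- Hidden illness among those recorded as not ill: h = p·u(1 − c) / (1 − r).
- With r̄ the mean of r over the two groups, the weighted rate is r̄·RR + (1 − r̄)·[1 + (RR − 1)h].
- Planned IRR = weighted rate (high) / weighted rate (recommended).

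**Example 1: p = 40% in both, u = 25% v 10%, RR = 2, c = 0.**
- r = 0.30 and 0.36; r̄ = 0.33.
- h = 0.10/0.70 = 0.1429 and 0.04/0.64 = 0.0625.
- Rates: 0.66 + 0.67 × 1.1429 = 1.4257 and 0.66 + 0.67 × 1.0625 = 1.3719.
- IRR = 1.039. The crude IRR is 1.4/1.4 = 1.000, so here the adjustment itself creates the error.
- With half recorded (c = 0.5): r = 0.35 and 0.38, r̄ = 0.365, h = 0.0769 and 0.0323, IRR = 1.4138/1.3855 = 1.020.
- With the shares reversed and c = 0: 1.3719/1.4257 = 0.962.

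**Example 2: p = 50% v 30%, u = 40% v 15%, RR = 3, c = 0.**
- r = 0.30 and 0.255; r̄ = 0.2775; h = 0.20/0.70 = 0.2857 and 0.045/0.745 = 0.0604.
- Rates: 0.8325 + 0.7225 × 1.5714 = 1.968 and 0.8325 + 0.7225 × 1.1208 = 1.642. IRR = 1.198.
- Crude IRR = 2.0/1.6 = 1.250, so the planned weighting removes (0.250 − 0.198)/0.250, about a fifth of the excess.

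**Planned IRR over all inputs (true value 1).**

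| Illness of first-contact children recorded before index | Equal comorbidity, 40–50% | Comorbidity 50% v 30% |
|---|---|---|
| None | 1.04–1.11 | 1.08–1.20 |
| Half | 1.02–1.06 | 1.04–1.10 |
| 80% | 1.01–1.02 | 1.02–1.04 |
| None, first-contact shares reversed | 0.91–0.96 | 0.99–1.00 |

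**With a no-prior-record indicator added (c = 0).** The strata are first contact, known ill and known well. Equal-comorbidity cases return to 1.00. In Example 2 the strata have weights 0.275, 0.2775 and 0.4475, and the first-contact rates are 1 + 2 × 0.5 = 2.0 and 1 + 2 × 0.3 = 1.6. The IRR is (0.275 × 2.0 + 0.8325 + 0.4475)/(0.275 × 1.6 + 0.8325 + 0.4475) = 1.83/1.72 = 1.064. The unequal cases run from 1.025 to 1.064.

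The near-null values with reversed shares and unequal comorbidity are two errors offsetting each other. With u = 15% v 40% and RR = 3, the indicator gives (0.55 + 0.9075 + 0.4225)/(0.44 + 0.9075 + 0.4225) = 1.88/1.77 = 1.062, which exposes the remaining confounding by illness.

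**The case against.** A reader might infer that every sick child new to the network is weighted as healthy and that the high-dose IRR is therefore inflated. The documents do not support either step.

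- **Same-stay data count.** All pre-index data include earlier entries from the index stay, and 5.9.1.1 expressly admits AED or benzodiazepine administration in hospital. Section 5.3.1 expects detailed inpatient records. The gap is history not recorded before the first IV dose. As the table shows, this shrinks the bias but does not remove it.
- **Direction is not given.** Section 5.1 assumes loading-dose children are more often in refractory status epilepticus. That such children more often arrive as emergencies or transfers is a further inference. They could equally be long-followed patients of the epilepsy centres named in 5.9.4. Reversing the shares takes the IRR below 1.
- **Section 5.9.2 speaks of the diagnosis of interest.** It may have been written for outcomes, and it does not cover medications or seizure counts; prior seizure number is listed only if available. The point is therefore confined to diagnosis covariates, for which no other rule is stated.
- **The look-back window is unsettled** between 5.3.2 and 5.5.3. An empty record is possible under either.
- **Limitations and quality checks exist.** Section 5.9.4 admits missing comorbidities, and 5.7.1 describes study-specific checks on missing data and variation across subsets. These are generic and do not test recording by dose group.
- **A statistical analysis plan could add such covariates.** It could, but the protocol itself fixes a named list and states the equal-recording assumption, and both can be assessed as written.

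**Conclusion.** The point holds in a limited form. The score cannot separate a child known to be free of a condition from one with no prior record, and the protocol relies on equal recording between dose groups without testing it. The weighted IRR is biased if first contact, or the illness hidden by it, is related to dose group. If neither is, there is no bias.

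Size and sign are unknown, because the documents give neither first-contact shares by dose group nor the amount of history captured in the index stay. Under the assumed inputs the error runs from about 1% to 20% upward and can be up to 9% downward; with substantial same-stay recording it is a few percent. No stated figure in the protocol is wrong. This is a worthwhile, inexpensive improvement to the covariate set, not a flaw that invalidates the design.

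**What to change.** 1. Add to the 5.9.1.1 covariates an indicator for no network encounter before the index admission, plus grouped look-back length or number of earlier encounters.
2. Show both by dose group in the balance table.
3. Add to 5.9.1.4 one sensitivity analysis limited to children with at least one earlier encounter. Infants too young to have one are handled by the indicator.
4. In 5.9.4, replace the equal-recording assumption with the result of this check.
5. Reconcile 5.3.2 and 5.5.3 on the covariate look-back window.

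The new covariates come from encounter data already held, and nobody is excluded from the main analysis. The cost is slightly less precision and a smaller sample in the restricted run. The indicator does not remove bias when hidden illness itself drives dose (up to 1.06 remains in the unequal case), which is why the restricted run is needed as well.

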## 5 METHODOLOGY

### 5.1 Study design

This will be a retrospective cohort study that will use data from the PEDSnet database to estimate the incidence of select medical events for 8 SOCs and 3 SMQ terms and specific medical events included in these broad categories, and examine the effect of increasing IV LCM loading dose on the incidence of these select medical events. The study will also compare the incidence of the selected medical events in pediatric patient (aged  $\geq 1$  month  $< 17$  years) treated with higher IV LCM doses (including UCB's defined loading dose) to the incidence of these events in pediatric patients treated with a recommended initial/maintenance IV LCM dose.

The study will use electronic healthcare records (EHR) data from the PEDSnet data network, collected from the earliest (2009) through the latest date that data are available (~2018) for each included patient. The cohort design will allow the identification of pediatric patients treated with higher IV LCM doses or a recommended initial/maintenance IV LCM dose, and the ability to follow them to identify the occurrence of outcomes of interest.

[figure not shown]
The study will consist of two mutually exclusive cohorts. The first cohort will consist of pediatric patients treated with higher IV LCM doses (including UCB's defined loading dose).

The second, the comparator cohort will comprise of pediatric patients treated with recommended initial/maintenance IV LCM dose. The index date will be defined as the initiation of a new IV LCM treatment episode/receipt of a higher IV LCM dose than known maintenance dose (described in detail in Section 5.3.1). The exposure period will be defined as the time between the index date (as defined above) and discontinuation of IV LCM (described in more detail in Section 5.5.4). Demographic characteristics will be defined at the index date. Baseline data will be used to define clinical characteristics, LCM exposure indications and identify prevalent cases of the selected medical events of interest. Each subject will be followed from the index date up to 30 days after discontinuing treatment with IV LCM. During the follow-up period, data will be assessed for occurrence of the select medical events, defined in Section 5.5.5.

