Electrocardiographic ventricular fibrillation (finding)	SCTID: 164896001
Sustained ventricular fibrillation (disorder)	SCTID: 429243003
History of ventricular fibrillation (situation)	SCTID: 161513002
Ventricular tachyarrhythmia (disorder)	SCTID: 6624005
Palpitations (finding)	SCTID: 80313002
Palpitations - rapid (finding)	SCTID: 248648003
Bumping heart (finding)	SCTID: 161968007

Table 3 SNOMED-CT concepts for the study	
Study outcome	SNOMED code
Pounding heart (finding)	SCTID: 248657009
Fluttering heart (finding) *	SCTID: 161969004
Palpitations with regular rhythm (finding)	SCTID: 428919002
Intermittent palpitations (finding)	SCTID: 102590007
History of palpitations (situation)	SCTID: 473122004
Skin and subcutaneous tissue disorders	
Stevens-Johnson syndrome (disorder)	SCTID: 73442001
Stevens-Johnson syndrome caused by drug (disorder)	SCTID: 403609001
Stevens-Johnson syndrome, toxic epidermal necrolysis spectrum (disorder)	SCTID: 768946000
Stevens Johnson syndrome AND toxic epidermal necrolysis overlap (disorder)	SCTID: 124911000119100
Stevens-Johnson and toxic epidermal necrolysis overlap syndrome caused by drug (disorder)	SCTID: 724833000
Toxic epidermal necrolysis	
Lyell syndrome (disorder)	SCTID: 768962006
Toxic epidermal necrolysis caused by drug (disorder)	SCTID: 402744003
Stevens-Johnson syndrome, toxic epidermal necrolysis spectrum (disorder)	SCTID: 768946000
Stevens Johnson syndrome AND toxic epidermal necrolysis overlap (disorder)	SCTID: 124911000119100
Stevens-Johnson and toxic epidermal necrolysis overlap syndrome caused by drug (disorder)	SCTID: 724833000
Angioedema	SCTID: 41291007
Giant urticaria (disorder)	SCTID: 400075008
Drug-aggravated angioedema-urticaria (disorder)*	SCTID: 241958006
Angioedema and/or urticaria (disorder)*	SCTID: 404177007
Urticaria	SCTID: 126485001
Acute urticaria (disorder)	SCTID: 402408009
Chronic urticaria (disorder)	SCTID: 51611005
Allergic urticaria (disorder)	SCTID: 40178009
Immunologic urticaria (disorder)	SCTID: 40370006
Contact urticaria (disorder)	SCTID: 19364004
Allergic contact urticaria (disorder)	SCTID: 402304007
Urticaria medicamentosa (disorder)	SCTID: 11012891000119106
Urticaria caused by serum (disorder)	SCTID: 89322006
Drug-aggravated angioedema-urticaria (disorder)*	SCTID: 241958006
Angioedema and/or urticaria (disorder)*	SCTID: 404177007

Table 3 SNOMED-CT concepts for the study	
Study outcome	SNOMED code

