### **5.9.1.2 Analysis of primary and secondary outcome measures**

Only the first occurrence of the event after the index date will be counted in analyses. For both the IV LCM group and comparator group, counts and frequency of events will be recorded. For both the IV LCM high dose group and comparator group, several incidence rates will be calculated. First, the overall incidence rate of any event of interest will be calculated. Second, incidence rates for each of the following events will be calculated individually: Cardiac disorders, Skin and subcutaneous tissue disorders, Nervous system disorders, Metabolism and nutrition disorders, Psychiatric disorders, Injury, poisoning and procedural complications, General disorders and administration site conditions, and Investigations, Drug reaction with eosinophilia and systemic symptoms syndrome, Severe cutaneous adverse reactions and Hypersensitivity events. Third, incidence rates for each subcategory of the abovementioned events and associated 95% confidence intervals will be calculated. The incidence rate of each event with associated 95% confidence interval will be calculated for the IV LCM high dose group and comparator group.

The numerator will be the total number of patients with the outcomes identified during the follow-up period. The denominator will be in patient-days. That is, the total summation of individual patient-days at risk up to the first occurrence of the AE of interest for subjects with

that AE, and the total patient-days at risk calculated up to the censoring date i.e. discontinuation of IV LCM plus 30 days or loss to follow-up for those subjects not experiencing that AE. Incidence rates will be presented with a 95% exact confidence interval based upon the Poisson distribution or another relevant model if there is nonconvergence. It is important to note incidence rates per time at risk are based on a constancy assumption. That is, the rates per unit of time assume that the event occurs with a constant rate over time. Events that are more likely to occur early or late relative to the initial exposure or with an increasing or decreasing hazard rate over time would not meet the constancy assumption and these rates should be viewed with caution. The person time for each patient will be calculated as the total number of days of follow-up as described in Section 5.3.3 .

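### The main analysis has no new-onset rule, so conditions present before the index dose can count as incident events, and the list of pre-existing events omits three primary outcome categories

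*Protocol*

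**What the plan says.** Section 5.1 says that baseline data will be used to "identify prevalent cases of the selected medical events of interest". Section 5.3.2 keeps such children in the study: "Preexisting medical events of interest are not exclusion criteria in this study; instead, they will be used to characterize the patient population".

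Section 5.9.1.2 sets the counting rule: "Only the first occurrence of the event after the index date will be counted in analyses". It adds: "The numerator will be the total number of patients with the outcomes identified during the follow-up period". Time at risk runs to that first event or to censoring. Nothing in the section removes a child who already had the condition, from either the numerator or the patient-days.

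Table 3 (Section 5.5.5) contains four history codes inside outcome definitions. Those for urticaria and angina carry a prevalent mark. "History of ventricular fibrillation (situation") and "History of palpitations (situation") carry none. The table also lists chronic and permanent atrial fibrillation and chronic urticaria.

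Section 5.5.3 gives a closed list of pre-existing events of interest: "cardiac conditions, dermatologic conditions, vascular conditions, injury, poisoning and procedural complications, general disorders and administration site conditions, investigations", followed by the three SMQ categories. The propensity score list in Section 5.9.1.1 repeats it.

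Three provisions bear on the problem:
- Section 5.9 stratifies all analyses by pre-existing events. Section 1 makes this depend on sufficient numbers.
- Section 5.9.1.4 excludes children with pre-existing events, as a sensitivity analysis.
- Section 5.9.1.1 includes a generic covariate for diagnosed conditions in the propensity score.

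**The concern.** An incidence rate needs a numerator of new events and a denominator of people free of the event. Here the prevalent cases are to be identified, but the main analysis does nothing with them. Table 4 says "Final diagnoses are recorded at each encounter", so a known gait disorder, arrhythmia, feeding problem or behaviour disorder entered again during the index admission meets the event definition. A history code meets it by describing the past.

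Two things are at stake. The reported rates, which are the primary result, would mix old and new conditions. The comparison of dose groups would also be distorted, and it could hide a dose effect or create one. For nervous system, metabolism and nutrition, and psychiatric disorders, the planned safeguards may not apply at all, because the list that drives them leaves these categories out.

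**Working it through.** **1. Which outcomes the pre-existing list covers.** Section 5.5.1 has 11 primary categories (8 SOCs and 3 SMQs). The list in Section 5.5.3 has nine entries.

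| Primary category (5.5.1) | In the list in 5.5.3 and 5.9.1.1? |
|---|---|
| Cardiac; skin; injury and procedural; general and administration site; investigations | Yes |
| DRESS; severe cutaneous reactions; hypersensitivity | Yes |
| Nervous system; metabolism and nutrition; psychiatric | No |

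Eight of 11 are covered and three are not. The ninth entry, vascular conditions, is not an outcome. Section 5.3.2 refers to Section 5.5.6 for the list, and Section 5.5.6 refers back to Section 5.5.3, so there is no fuller list elsewhere.

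**2. Direction and size.** The Protocol states no event rate, prevalence or power, so there is no figure to reproduce. The only count is 875 children before the full criteria (Section 5.9.3). All risks, ratios and carry-over shares below are assumptions.

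Model, per child:
- *T* = 37 days, the maximum follow-up in Section 5.3.3
- *p* = true comparator risk over *T*; hazard *h*0 = −ln(1 − *p*)/*T*; high-dose hazard *h*1 = *R* × *h*0
- *q* = share of children whose old condition is recorded again on day 1 and counted, contributing half a day
- Events = *q* + (1 − *q*)(1 − e^(−*hT*))
- Patient-days = 0.5*q* + (1 − *q*)(1 − e^(−*hT*))/*h*
- Observed rate = events / patient-days

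Worked case: *p* = 5%, *R* = 2, *q* = 10% in both groups.
- *h*0 = 0.051293/37 = 0.001386 per day; *h*1 = 0.002773
- Comparator: events 0.10 + 0.90 × 0.05 = 0.145; patient-days 32.51; rate 0.00446; inflation 0.00446/0.001386 = 3.22
- High dose: events 0.10 + 0.90 × 0.0975 = 0.1878; patient-days 31.70; rate 0.00592
- Observed IRR = 0.00592/0.00446 = 1.33

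Equal carry-over, true IRR 2:

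| *p* | *q* = 2% | *q* = 5% | *q* = 10% | *q* = 20% |
|---|---|---|---|---|
| 2%: inflation / IRR | 2.02 / 1.50 | 3.63 / 1.28 | 6.55 / 1.16 | 13.45 / 1.08 |
| 5%: inflation / IRR | 1.41 / 1.72 | 2.05 / 1.50 | 3.22 / 1.33 | 5.98 / 1.19 |
| 10%: inflation / IRR | 1.20 / 1.84 | 1.53 / 1.67 | 2.11 / 1.50 | 3.49 / 1.32 |

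Unequal carry-over, *p* = 5%:

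| *q*, high dose vs comparator | Observed IRR if truth is 1 | Observed IRR if truth is 2 |
|---|---|---|
| 10% vs 5% | 1.57 | 2.08 |
| 20% vs 5% | 2.92 | 3.46 |
| 5% vs 10% | 0.64 | 0.96 |

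Results with *T* = 7 days are nearly identical. With *q* = 0 the model returns the true values.

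**3. Illustrative loss of power.** Split the 875 evenly, about 437 per group, and compare proportions of 5% and 10%: power is 80%. With 10% equal carry-over the proportions become 0.10 + 0.90 × 0.05 = 14.5% and 0.10 + 0.90 × 0.10 = 19.0%, and power falls to 43%.

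**The case against.** **The plan already handles this.** In part it does. The stratum without pre-existing events is close to the analysis wanted here, and an exclusion analysis is planned. A reader might infer that the sensitivity analysis is the only correction; the stratification shows otherwise. But the stratification depends on numbers according to Section 1, both provisions rest on the incomplete list, and neither is specific to an outcome: a child with an earlier rash would leave the cardiac analysis too.

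**The three omitted categories are covered elsewhere.** Section 4 defines the events of interest as all 11 categories, and the generic diagnosis covariate in the propensity score could include them. So a reader should not infer that they are wholly unhandled. The closed list in Section 5.5.3 still conflicts with Section 4. Weighting can balance prevalent cases between groups but cannot take them out of a numerator.

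**Table 3 is provisional.** Section 5.5.5 says that its concepts will be reviewed and case definitions developed with clinicians, and two history codes are already marked. That shows intent, but the mark is inconsistent and its effect is not stated. Section 5.4.1 says that SNOMED-CT lets drug symptoms be separated from chronic conditions, but gives no rule for doing so.

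**A SAP could supply the new-onset rule.** It could. However, the Protocol itself fixes the numerator and the time at risk, and as fixed they admit prevalent cases.

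**Re-recording is not shown.** This stands. Recording diagnoses at each encounter does not prove that old ones are entered again, and acute terms such as torsade de pointes or injection-site events should carry over little.

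**Ratios are simply diluted.** A reader might infer that carried-over cases always pull the IRR toward 1. That needs about equal carry-over in both groups. Section 5.1 expects loading-dose patients to be more often in refractory status epilepticus, so equality cannot be assumed.

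**Exclusion can do harm.** Dropping every child with any earlier event in the same SOC would lose real worsening, such as earlier first-degree block followed by complete block. This stands, and it shapes the fix.

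**Conclusion.** The concern holds in a limited form. The main analysis has no rule that restricts events to new onset or worsening, two history codes count as outcomes without a prevalent mark, and the list of pre-existing events does not match the primary outcomes. Where old conditions are recorded again after index, rates are inflated. The direction of the IRR bias is not known: toward 1 under equal carry-over, either way otherwise.

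The size cannot be derived from the Protocol. Over the equal carry-over shares assumed above (2% to 20%), comparator rates are inflated between 1.20-fold (10% risk) and 13.45-fold (2% risk). These figures rest on a constant hazard and on day-1 re-recording. They show sensitivity and are not a forecast. The point matters because incidence is the primary objective and the correction is cheap.

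**What to change.** 1. In Section 5.9.1.2, count for each outcome only new-onset or worsened events: exclude from that outcome's numerator and time at risk any child with the same preferred term recorded before index. Build the SOC rates from these preferred-term events, not by excluding on any earlier event in the SOC, so that progression to a different term still counts. Report the all-patient analysis alongside.
2. In Table 3, treat all four history codes as baseline only, and say so.
3. Align the pre-existing lists in Sections 5.5.3 and 5.9.1.1 with all 11 primary categories, so that the stratification and the sensitivity analysis reach nervous system, metabolism and nutrition, and psychiatric disorders.

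The cost is wording and code lists. Section 5.3.2 already plans to use all data before index, so no new data are needed. The downside is fewer children at risk for outcomes with common earlier codes; showing the all-patient analysis beside it keeps that loss visible.
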